6.6.3 Clinical Laboratory Evaluations

Clinical laboratory evaluation will be performed at screening, prior to administration of Flortaucipir injection, and after completion of Flortaucipir imaging for each of the scan sessions, including the makeup scan session if the original planned scan session fail.

Tests will include:

- Hematology (5 mL EDTA): hemoglobin, hematocrit, RBC, WBC, MCH, MCHC, neutrophils, bands, lymphocytes, monocytes, eosinophils, basophils, platelets, morphology, MCV, and RBC morphology.
- Chemistry (6 mL blood): total bilirubin, alkaline phosphatase, ALT (SGPT), AST (SGOT), urea nitrogen, creatinine, glucose, uric acid, calcium, phosphorus, total protein, albumin, total cholesterol, triglycerides, sodium, potassium, bicarbonate, chloride, magnesium, globulin, GGT.
- Urinalysis (10 mL, urine): Samples will be used to assess glucose, RBC, WBC, specific gravity, pH, protein, ketones, urobilinogen, blood, nitrite, microscopic, color, bilirubin, casts, epithelial cells, leukocyte, esterase, and bacteria.
- Serum beta hCG, qualitative: performed at screening for females of childbearing potential who are not surgically sterile. A serum pregnancy test may also be obtained prior to injection at the Imaging Visit if required by the local site.
- Urine beta hCG: performed at the imaging visit(s) prior to injection for females of childbearing potential (defined as pre-menopausal, less than 2 years post-menopausal or not surgically sterile).

- ApoE Genotyping (10ml, blood): will be performed at the initial Flortaucipir imaging session for those subjects whose ApoE results are unknown.

Baseline for clinical laboratory evaluations will be calculated as described in section 6.3. Change from baseline for continuous post-baseline assessments will be calculated as the result at the visit minus the baseline value. For applicable laboratory tests, laboratory values will be defined as low, normal, or high relative to the normal reference ranges for each subject's age and sex. Criteria for potentially clinically significant laboratory results are defined in Appendix 1 of the SAP. A result will be considered potentially clinically significant if the result occurs post-baseline and no test results at or prior to baseline for the parameter in question meet the same criteria for potential clinical significance.

6.6.4 Other Observations Related to Safety

6.6.4.1 Vital Signs

Vital signs (pulse rate, respiratory rate, and supine blood pressure) will be taken at the following time points:

- Screening visit
- Florbetapir F18 Imaging Day
 - immediately prior to injection of florbetapir F 18
- Flortaucipir Imaging Day
 - Immediately prior to the administration of Flortaucipir injection
 - Within 5 minutes after completion of injection of Flortaucipir injection
 - After the completion of imaging prior to discharge

Temperature will be obtained at the following time points:

- Flortaucipir Imaging Day
 - Immediately prior to the administration of Flortaucipir injection
 - After the completion of imaging prior to discharge

Baseline for vital signs will be calculated as described in Section 6.3. Change from baseline for post-baseline assessments will be calculated as the result at the visit minus the baseline value. Criteria for potentially clinically significant vital sign results are defined in Appendix 2 of this SAP. A measurement will be considered potentially clinically significant if the measurement occurs post-baseline and no measurements at or prior to baseline for the parameter in question meet the same criteria for potential clinical significance.

6.6.4.2 *Electrocardiogram (ECG)*

A resting 12-lead ECG will be recorded at screening. At the Flortaucipir imaging visits the ECGs will be taken at the following time points:

- Two ECGs will be taken at approximately 5 minutes apart immediately prior (within approximately 10 minutes) to Flortaucipir injection administration.
- One ECG will be taken immediately (within approximately five minutes) after completion of Flortaucipir injection.
- One ECG will be taken after completion of the PET scan prior to discharge.

Baseline for ECGs will be calculated as described in section 6.3. Change from baseline for post-baseline assessments will be calculated as the result at the visit minus the baseline value. Criteria for potentially clinically significant ECG results are defined in Appendix 2 of this SAP. A result will be considered potentially clinically significant if the result occurs post-baseline and the baseline result for the parameter in question does not meet the same criteria for potential clinical significance.

6.7 **Pharmacodynamics Parameters**

No pharmacodynamics parameters will be collected during this study.

7 **STATISTICAL METHODS**

7.1 **General Methodology**

All values will be summarized by the four diagnostic groups: young cognitively normal (YCN) subjects (healthy volunteers ≥ 20 years of age and ≤ 40 years of age), old cognitively normal (OCN) subjects (healthy volunteers ≥ 50 years of age), patients with AD, patients with MCI, and overall. Frequency distributions including counts and percentages will be included for all categorical outcomes. Summary statistics including mean, standard deviation, median, minimum and maximum values will be presented for all continuous outcomes. Unless otherwise specified, hypothesis testing will be two-sided with type I error rate of 0.05.

All statistical analyses will be performed using SAS® version 9.3 or higher.

7.2 **Adjustments for Covariates**

Not applicable for the primary analyses.

7.3 **Handling of Dropouts or Missing Data**

Dropout subjects will not be replaced in this study. For situations with no rules for handling missing data, the default will be no imputation.

A likelihood-based mixed effects model for repeated measures will be used to handle missing longitudinal follow up cognitive measurements, or flortaucipir SUVr data. The model parameters are simultaneously estimated using restricted likelihood estimation incorporating all of the observed data. Estimates have been shown to be unbiased when the missing data are missing at random and when there is ignorable non-random missing data.

Repeated measures analyses will only use data from visits where the data was scheduled to be collected. When subjects discontinue from the study early, there may be efficacy data measurements at visits where the variables were not scheduled to be collected. These data will appear in listings only.

7.4 Interim Analyses and Data Monitoring

No interim analysis or data monitoring is planned for this study

7.5 Multi-center Studies and Pooling of Centers

This study will be conducted in approximately 30 centers. The data from all centers will be pooled. The pooled data will be analyzed and presented.

7.6 Multiple Comparisons/Multiplicity

For the exploratory (first) phase analysis, no adjustment for multiplicity will be performed when analyzing the differences among diagnostic groups.

7.7 Active-Control Studies Intended to Show Equivalence

Not applicable to this study.

7.8 Examination of Subgroups

Flortaucipir SUVr values will be further investigated stratified by age group (≥ 75 vs. < 75).

8 STATISTICAL ANALYSIS

8.1 Disposition of Subjects

The number and percentage of subjects who were treated, who completed the study, and who discontinued from the study, as well as the reasons for discontinuing, will be

summarized. Subjects will be considered to have completed the study if they have completed all three flortaucipir imaging sessions and clinical visits.

Data on screening failures (subjects who signed informed consent but were not entered into the trial) were not collected on the CRF, are not included in the database and will not be presented.

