Subjects who are ≥ 50 years of age will return for follow-up visits at 9 (+/-2) months and 18 (+/-2) months following the initial ¹⁸F-AV-1451 scan. Cognitive assessments and updates to concomitant medications and medical history will be collected at each follow-up visit. Subjects in the Exploratory Phase will also have follow up ¹⁸F-AV-1451 scans and MRI, including both volumetric and standard clinical sequences. A sub-set of subjects in the Exploratory Phase may have the option to have an additional resting state functional (rsf)MRI sequence scan in addition to the volumetric and standard clinical sequences at both the screening MRI and follow-up MRIs. All follow-up procedures should be collected within the specified visit window (See Section 7.1.4). Subjects or their designated decision maker will be contacted by phone at 5 and 14 months following the initial ¹⁸F-AV-1451 scan to collect updated concomitant medications and medical history.

Avid personnel will be blinded to the Confirmatory Phase longitudinal cognitive data. Avid personnel will also remain blinded to the PET scans (both florbetapir and ¹⁸F-AV-1451) performed on subjects in the Confirmatory Phase with the exception of periodic quality assurance (QA) assessments of a random subset of image data (not to exceed 20% unless issues identified that warrant additional review). These QA reviews will serve to ensure image quality and data integrity for the scans collected and managed by the imaging core laboratory. Avid staff performing the PET scan QA assessment will not be aware of diagnostic group or cognitive test scores for the subjects/images being reviewed.

Florbetapir F 18 PET Imaging Session:

For the florbetapir F 18 PET imaging session, an intravenous catheter will be placed for IV administration of Florbetapir F 18 Injection. Subjects will receive a single IV bolus injection target dose of 370 MBq (10 mCi) of Florbetapir F 18 Injection followed by a saline flush. At approximately 50 minutes following injection, a continuous 10-minute brain scan (2 acquisitions of 5 minute duration) will begin.

Adverse events will be continuously monitored during the florbetapir F 18 PET imaging session. A physician or physician designee must evaluate the subject for adverse events prior to injection and prior to discharge from the imaging center. Subjects who experience an adverse event will not be discharged from the imaging center until the event has resolved or stabilized.

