4.3 Method of Assignment of Subjects to Treatment Groups

Florbetapir F 18:

All subjects will receive a single IV bolus administration target dose of 370 MBq (10 mCi) of florbetapir F 18 injection.

Flortaucipir:

All subjects except for young cognitive normal (YCN) subjects will receive a single IV bolus administration target dose of 370 MBq (10 mCi) of Flortaucipir injection at each of the baseline, 9 months, and 18 months visits. YCN subjects will only receive a single IV bolus administration of Flortaucipir injection with a target dose of 370 MBQ (10 mCi) at baseline visit.

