4.5 Determination of Sample Size

A total of 230 subjects (80 cognitively healthy volunteers, 80 MCI and 70 AD) will be enrolled in the Exploratory Phase of this study. To explore the Flortaucipir SUVR values across age strata among cognitively healthy subjects, these subjects will be divided into 5 age groups as 20-40 years old, 50-59 years old, 60-69 years old, 70-79 years old and 80 years old or above. There will be 15 subjects in each of the 50 or older age groups and about 20 subjects from age group 20-40 years old. From a preliminary analysis of study T807000, the standard deviation (SD) of SUVR from combination region of interest (ROI) was 0.06 for subjects with low probability of AD. Therefore assuming a 0.06 SD, a sample of 15 subjects will give an approximately 90% probability to observe a 95% confidence interval as accurate as +/-0.04 around the point estimation.

From previous studies, the amyloid positive rate is approximately 50% among MCI patients and approximately 80% from AD subjects. Therefore 80 MCIs and 70 ADs will likely result in 40 amyloid positive MCIs and 56 amyloid positive ADs. Also from study T807000, the combination ROI SUVR difference between CN and AD was 0.39, with a pooled SD of 0.27. Assume a pooled SD of 0.30, a sample of 60 CNs and 56 amyloid positive ADs will give a 90% power to detect a 0.18 difference between the CN and AD groups.

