8.6.2 Exploratory Phase, Longitudinal Analysis

8.6.2.1 Analysis of Primary Efficacy Variable

Mixed Model Repeated Measures for Evaluation of Flortaucipir SUV_r over time

Descriptive summary statistics for Flortaucipir SUV_r will be provided by amyloid beta status (AB+, AB-) at baseline, 9 month, and 18 month across all subjects.

Change from baseline for Flortaucipir SUV_r will be estimated using repeated measures models for all subjects except for YCN subjects (who do not have follow-up flortaucipir scans at 9 months and 18 month). Due to the concern of unequal variance for flortaucipir SUV_r changes by amyloid status, the model will be run for AB+ subjects only, and for AB- subjects only separately. For this analysis, time will be considered to be categorical variable. A mixed model will be run with MUBADA SUV_r change from baseline as dependent variable, baseline MUBADA SUV_r and age, and visit as independent variables. In order to appropriately model the within subject covariance, the covariance structure must be pre-specified. Each model should be fit using the unstructured covariance structure. If this structure does not converge, covariance structure in the order as auto-regressive, Toeplitz structures and the compound symmetry will be used.

The LS means of MUBADA SUV_r change at each visit from the model will be displayed along with the corresponding 95% confidence intervals. In addition, p-values will be

provided for testing that whether or not the LS means at each visit is significantly different than zero.

Spaghetti plots will be generated to display the relationship of Flortaucipir SUVr change across the follow up visits, by each subject. The plot will use MUBADA SUVr as y-axis, subjects' age at each visit as x-axis, and color code according to amyloid status.

Explore Factors Associated with Flortaucipir SUVr Change using Multivariate Analysis

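### The SAP's single completion rule requires three flortaucipir sessions, so young controls, who have one by design, can never count as completers

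*SAP*

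**What the plan says.** SAP 8.1 (Disposition of Subjects) gives one definition of completion for all subjects: they must have "completed all three flortaucipir imaging sessions and clinical visits". It asks for counts and percentages of subjects treated, completed and discontinued, with reasons for discontinuing. SAP 8.3.1 puts disposition on the enrolled population, and SAP 7.1 asks for summaries by YCN, OCN, MCI and AD, and overall.

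The schedule differs by group. Under SAP 4.3, everyone except YCN receives "Flortaucipir injection at each of the baseline, 9 months, and 18 months visits", whereas "YCN subjects will only receive a single IV bolus administration of Flortaucipir injection", at baseline. SAP 8.6.2.1 repeats this when it sets the longitudinal model, leaving out "YCN subjects (who do not have follow-up flortaucipir scans at 9 months and 18 month".

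The limit on visits, as distinct from injections, is in Protocol 5.1 and SAP 4.1. Protocol 5.1 says that subjects of at least 50 "years of age will return for follow-up visits at 9 (+/-2) months and 18 (+/-2) months". SAP 7.1 defines YCN as healthy volunteers aged 20 to 40, so none of them reaches that age limit.

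**The concern.** A YCN subject who does everything the study asks still fails the completion rule, on both the imaging part and the visit part. The SAP takes YCN out explicitly where the schedule or age makes it necessary, for example in the cross-sectional ANOVA (8.6.1.1) and the longitudinal SUVr model (8.6.2.1). The absence of any such provision in 8.1 looks like an oversight, and a programmer following the text would produce a misleading table.

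What is at stake is how retention reads. The longitudinal component estimates change over 18 months with a likelihood-based repeated-measures model, and SAP 7.3 relies on a missing-at-random argument. Readers judge that argument partly from the completion figures. An overall figure pulled down by subjects who were never due to return understates retention.

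**Working it through.** **Inputs**

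| Quantity | Value | Source |
|---|---|---|
| YCN planned | about 20 | SAP 4.5: "about 20 subjects from age group 20-40 years old" |
| OCN planned | 60 (four age groups of 15) | SAP 4.1, 4.5 |
| MCI, AD planned | 80, 70 | SAP 4.5 |
| Flortaucipir sessions, YCN | 1 | SAP 4.3, 8.6.2.1 |
| Flortaucipir sessions, other groups | 3 | SAP 4.3 |
| 9- and 18-month visits, YCN | 0 | Protocol 5.1, SAP 4.1 |
| Disposition population | enrolled, YCN included | SAP 8.3.1 |

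**Step 1: reproduce the stated total.** SAP 4.5 gives "A total of 230 subjects (80 cognitively healthy volunteers, 80 MCI and 70 AD" plus a closing bracket. By group: 20 + 60 + 80 + 70 = 230, which agrees.

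**Step 2: apply the rule as written, with no dropout.** The highest possible completion rate is the number scheduled for three sessions divided by the number enrolled.

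- YCN: 0/20 = 0%.
- Overall: (230 − 20)/230 = 210/230 = 91.3%.
- Shortfall due to the rule alone: 20/230 = 8.7 percentage points.

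**Step 3: allow for dropout.** No dropout rate is given for the Exploratory Phase. Protocol 8.1.1.2 assumes about 20% over 18 months for the Confirmatory Phase. I take 10% to 30% in subjects aged 50 or older as an illustrative range. With dropout d, completers in that cohort number 210 × (1 − d). The group-specific column assumes that all 20 YCN finish their own schedule.

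| Assumed d | Completers aged ≥ 50 | Overall, rule as written | Overall, group-specific rule | 50-or-older denominator | YCN among non-completers, rule as written |
|---|---|---|---|---|---|
| 0% | 210 | 210/230 = 91.3% | 230/230 = 100% | 210/210 = 100% | 20/20 = 100% |
| 10% | 189 | 189/230 = 82.2% | 209/230 = 90.9% | 189/210 = 90% | 20/41 = 49% |
| 20% | 168 | 168/230 = 73.0% | 188/230 = 81.7% | 168/210 = 80% | 20/62 = 32% |
| 30% | 147 | 147/230 = 63.9% | 167/230 = 72.6% | 147/210 = 70% | 20/83 = 24% |

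The gap between the two overall columns is 8.7 points in every row.

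**Step 4: check what uses completion status.** The safety population (SAP 8.3.2) depends on injection. The efficacy population (8.3.3) depends on injection plus valid flortaucipir imaging data. The longitudinal SUVr model already excludes YCN (8.6.2.1). The longitudinal cognitive analyses are restricted to MCI/AD or amyloid-positive subjects (8.6.2.4). None of them uses the 8.1 definition.

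**The case against.** The strongest reply is that the damage is slight and visible. Disposition is shown by group, so the OCN, MCI and AD columns are correct, and the rate for subjects aged 50 or older can be had by adding them. A 0% in a group that the same SAP says has no follow-up scans is plainly structural. No analysis population or endpoint depends on it. All of this stands, and it is why the point is minor. It does not make the definition right: the YCN cell and the overall column would still be wrong.

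A reader might go further and infer that the table will show an inflated discontinuation rate, or that sites will have to find reasons for discontinuations that never happened. The documents do not support that. SAP 8.1 lists completing and discontinuing as separate items and does not define one as the absence of the other. Protocol 5.5 treats discontinuation as an event with a date and reason on the CRF, and Protocol 8.2 lists subjects who stopped participating before completion. A YCN subject who finishes the baseline schedule has no such event. As written, these subjects could fall in neither category, so the completed and discontinued counts might not account for everyone.

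A further caution concerns the remedy. It is tempting to call YCN complete after the flortaucipir session and its follow-up call. Every subject also has a florbetapir session. The two may be done in either order and up to 60 days apart (Protocol 7.1.3, SAP 4.1). A YCN subject scanned with flortaucipir first who never returned for florbetapir would then count as a completer, which would hide a real dropout.

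**Conclusion.** The point holds, at minor severity. SAP 8.1 sets a completion rule that YCN subjects cannot meet. YCN completion is 0% whatever the final counts. On the planned numbers, overall completion is capped at about 91.3%, a shortfall of 8.7 points that the rule alone creates.

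The 20 and 230 are approximate planned sizes. The actual denominator will be everyone who consented and has data in the clinical database, so the percentages are planning illustrations. The rates under dropout rest on an assumed range. The effect stays within the YCN and overall cells of the disposition table. No efficacy or safety conclusion changes.

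**What to change.** In SAP 8.1, define completion as finishing all procedures scheduled for the subject's group:

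- **YCN:** the baseline procedures, both the florbetapir and the flortaucipir session, and the post-scan call after each.
- **Subjects aged 50 or older:** the existing rule of three flortaucipir sessions and the clinical visits.

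State whether the 5- and 14-month phone calls apply to YCN. Protocol 7.1.5 and SAP 4.1 give them for subjects generally, with no age limit, so the end of YCN participation is not settled by the current text. Report the longitudinal completion rate on the 50-or-older denominator (about 210 planned).

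The cost is a short wording change in SAP 8.1 and the matching table specification. It needs no new data and no change to trial conduct.

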8.2 Protocol Deviations/Violations

Subjects who entered the study even though they did not satisfy one or more of the inclusion/exclusion criteria will be listed. Deviations/violations from the protocol will be documented, the Avid/contract research organization (CRO) monitor will then be informed and a course of action will be agreed upon.

8.3 Analysis Populations

8.3.1 Enrolled Population

The enrolled population will consist of all subjects who signed informed consent and have data captured in the clinical database. Disposition information will be summarized using the enrolled population.

8.3.2 Safety Population

The safety population will consist of all subjects that received either an injection of flortaucipir or florbetapir dosage. The summary of safety will be defined according to the study drugs subjects received: for the safety summary of flortaucipir scans, the safety population consist of all subjects that received an injection of Flortaucipir; for the safety summary of florbetapir scan, the safety population is defined as all subjects that received and injection of Florbetapir injection.

All baseline and safety endpoints will be summarized and efficacy endpoints listed using the safety population.

8.3.3 Efficacy Population

The efficacy population will include all subjects from safety population that received an injection of Flortaucipir plus valid flortaucipir imaging data available (either visual reads or SUV_r).

All analyses involving amyloid imaging outcomes will be based on the efficacy population. For flortaucipir SUV_r related analyses, any scans deemed to be unquantifiable due to technical reasons will be excluded from analyses.

8.4 Demographic and Other Baseline Characteristics

All baseline summaries will be based on the safety population.

Frequency distributions and summary statistics for demographic and baseline variables will be presented by diagnostic groups, and for all subjects combined. Key demographic and baseline characteristics to be summarized include: age, gender, race, ethnicity, height, weight, BMI, education, alcohol history, recreational drug use history, smoking history, medical history, family disease history, cognitive assessments, worst brain injury history, physical examination, and neurological examination.

All demographic and baseline characteristics data will be presented in listings.

